1.3.2. Study plan

The study start is defined as the date of the first visit of the first patient, corresponding to informed consent form (ICF) signature. It will be divided into the following periods for each patient of Arm A:

- **Screening visit**

The screening eligibility criteria will be checked after the patient informed consent is obtained.

- **Inclusion period**

The inclusion and exclusion criteria will be checked. The inclusion period can last up to 15 days before starting the LID period. The patient is included when he/she has met all the inclusion criteria.

- **S64315 lead-in dose period**

The lead-in dose period will last 2 weeks. S64315 LID1 will be administered on D-13 at 25 mg and LID2 on D-6 at 50 mg. LID1 and LID2 doses will be fixed all along the study.

- **Combination treatment period**

A treatment cycle will consist of 28 days for patients treated with S64315 in combination with azacitidine during the dose escalation phase I part:

- Weekly schedule for S64315 on CxD2, CxD9, CxD16 and CxD23.
- Daily schedule for azacitidine from CxD1 to CxD7 followed by a 21-day rest period.

The planned duration of combination treatment is until disease progression, unacceptable toxicity, treatment failure (defined as failure to achieve complete remission (CR), complete remission with incomplete haematologic recovery (Cri), partial response (PR), or morphologic leukaemia-free state (MLFS) after at least 6 cycles of study treatment) or patient/physician decision. In case of myelosuppression within the context of non-active AML, a 4-week interruption of administration of one or both IMP(s) will be allowed for bone marrow recovery at the investigator's discretion after discussion and approval from the Sponsor. If the patient is benefiting from the study treatment according to the investigator's judgement and if it is in the patient's best interest to continue the combination of S64315 with azacitidine, the patient may remain on study treatment. In case the patient becomes eligible for transplant, patient's treatment discontinuation should be left at the investigator's decision.

- **Withdrawal visit (WV):**

Up to 28 days after the last dose of IMP

- **Post-withdrawal follow-up**

After the withdrawal visit, a contact or telephone call will be done for the patients:

- Every 3 months (± 15 days) from the WV and up to 6 months, except in case of consent withdrawal for the dose escalation phase I part.

- **End of Trial (EoT)**

The EoT is defined as the date of the last follow-up of the last patient (including a phone contact), or the date of the last contact attempt if the last patient is declared lost to follow-up.

[figure not shown]
Figure (1.3.2) 1 - Study plan for S64315 administration schedule in combination with azacitidine (dose escalation phase I part – Arm A)

Study treatments:

S64315 administered via IV infusion, weekly during the 2-week lead-in dose period on D-13 and D-6 and then on D2, D9, D16, D23 of each 28-day combination cycle

Azacitidine administered via SC injection, daily from D1 to D7, at the dose of 75mg/m² of each 28-day combination cycle

Study periods:

S64315 infusion on D-13, D-6, CxD2, CxD9, CxD16, CxD23
Azacitidine administration from CxD1 to CxD7
PK: pharmacokinetic measurements
PD: pharmacodynamics measurements
PG: optional pharmacogenomics measurements
WV: withdrawal visit

AZA: azacitidine
D: day
FU: post-withdrawal follow-up
LID: Lead-in dose
QW: Once Weekly
W: week

1.3.3. Type of randomisation

The assignment of a patient to a particular cohort will be coordinated by the Sponsor. No randomisation will be performed in this study.

1.4. Determination of sample size

No formal statistical power calculations to determine sample size were performed for this study. Overall, a maximum of 180 patients will be enrolled in the dose escalation phase I part of Arm A (up to 30 patients) followed by sub-arms A1 and A2 (50 per sub-arms, up to 150 patients overall). However, due to the stop of the dose escalation phase, the expansion part to sub-arms A1 and A2 will not be conducted.

2. ANALYSIS SETS AND SUBGROUPS

2.1. Analysis sets and subgroups

- Screened Set:

All patients who signed the ICF, whether they are included or not at the end of the screening period.

- Included Set (IS):

All patients who have signed the ICF, whose eligibility was confirmed at the end of the screening period, and who were included in the dose escalation phase I part of the study.

- Safety Set (SS):

All patients who have signed the ICF and who received at least one dose of IMP (S64315 or azacitidine) during dose escalation phase I part of the study. It will be used for all safety analyses.

For the safety analysis, patients will be analysed according to the treatment combination and dose level received at C1D1 (for azacitidine) and C1D2 (for S64315). Patients who only received LID will be analysed according to the dose of S64315 planned to be administered.

- Evaluable Set (DLTES):

All patients from the SS who are evaluable for DLT according to the DLT assessment at the end of cycle 1. A patient is not considered evaluable for DLT if he/she:

- Permanently discontinued treatment before C1D28 for reasons other than DLT.
- Did not undergo a DLT assessment at the end of Cycle 1.
- Did not receive the minimum exposure criteria i.e., minimum number of doses according to the dose administration schedule of both IMPs prescribed from study entry to DLTs assessment visit (end of Cycle 1 D28), unless treatment was stopped for a DLT (see [Table \(2.1\) 1](#)).
- If a patient received more than the assigned IMP doses from study entry to DLT occurrence during the DLT assessment period, non-evaluability criteria will be reassessed by Sponsor and investigator ([Table \(2.1\) 1](#)).

Table (2.1) 1 - Minimum number of S64315 and azacitidine doses to meet minimum exposure until the end of cycle 1

Schedule description	Minimum of doses of S64315/azacitidine
S64315 during the 2-week LID period (LID1 on D-13 and LID2 on D-6)	2 out of 2
S64315 (D2, D9, D16 and D23 in 28-day cycle)	3 out of 4
azacitidine (D1 to D7 in 28-day cycle)	5 out of 7

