10.2.6. Dose proposed by the model

The dose allocation will start at the dose combination of 50 mg and 75 mg/m² respectively for S64315 and azacitidine.

A maximum of 6 DLT-evaluable patients may be initially enrolled at a dose level, and a minimum of 3 DLT-evaluable patients must be treated at a given dose level before a new higher dose level may be evaluated.

All available data on DLTs, assessed starting from the LID period to C1D28 will be used for updating the model. Before making a dose allocation decision, all patients from a cohort must:

- have been treated with LID1 and LID2, 3 out of 4 S64315 infusions and 5 out of 7 azacitidine injections or
- have had a DLT within the LID period or the first cycle

If a patient is not eligible for inclusion in the Dose-Limiting Toxicity Evaluable Set (DLTES), she/he must be replaced.

If a DLT occurred at LID1, the DLT will be considered as relative to 25 mg of S64315 in monotherapy. If a DLT occurred at LID2, the DLT will be considered as relative to 50 mg of S64315 in monotherapy. In that case, the patient will be replaced to ensure the minimal number of patients needed in the cohort at the full tested dose. Those DLTs will be considered for dose recommendation during the EoC meeting.

At any time during the study, if DLTs occur in the first 2 evaluable patients of a cohort (whether it happened during the LID period or cycle 1), the BLRM could be updated in order to re-evaluate the current dose level before enrolment of any additional patients in the cohort. Once each cohort of patients is completed, the dose recommendation by the model will be based on posterior summaries including the mean, median, standard deviation, 95%-credible interval, and the probability that the true DLT rate for each dose lies in one of the following categories:

- [0,16%) under-dosing
- [16%,33%) targeted toxicity
- [33%,100%] excessive toxicity

Following the principle of EWOC, after each cohort of patients, the dose combinations fulfilling the EWOC criterion (i.e. it is unlikely (<25% posterior probability) that the DLT rate at the dose falls in the excessive toxicity interval) will be identified by the model. A dose not fulfilling the EWOC criterion cannot be recommended.

In addition, admissible dose increments for the next cohort will not exceed 100% of the previous dose of S64315.

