3.4. Safety endpoints

All safety analyses will be performed in the SS (resp. DLTES for DLT analysis) by treatment dose level combination and overall. The treatment period is defined from first IMP intake up to last IMP intake date + (*) days.

(*) 30 days for AE and death analysis, 28 days for clinical laboratory evaluation, vital signs and clinical examination, centralized ECG and LVEF analysis.

Qualitative data will be presented in number and percentage of patients per class, while quantitative data will be presented in mean, SD, min and max, median, Q1 and Q3.

Calculation rules for expressions of safety endpoints, as well as general definitions (such as value prior to treatment / under treatment, analysable value, first and last IMP intake dates...), are provided in [Appendix 4.1](#).

Calculation rules for safety endpoints and other specific definitions are provided in [Appendix 4.2](#).

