3.4.1. Dose limiting toxicity

Number and percentage of patients with at least one DLT before the end of the first cycle, type of DLT and listing of PTs, verbatim and worst grade of AE declared as DLT will be provided in the DLTES.

Listing of patients with at least one DLT, type of DLT and PTs, verbatim will also be provided in the DLTES.

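### The SAP's by-dose DLT table can count a lead-in DLT under a combination dose never given, whereas protocol 10.2.6 attributes it to 25 or 50 mg S64315 alone

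*SAP*

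**What the plan says.** **Columns.** For the Safety Set, SAP 2.1 states that "patients will be analysed according to the treatment combination and dose level received at C1D1" for azacitidine, and at C1D2 for S64315. One subgroup is handled differently: "Patients who only received LID will be analysed according to the dose of S64315 planned to be administered". These patients had one or two S64315 infusions (25 mg, then 50 mg) and no azacitidine. The lead-in doses are the same in every cohort (SAP 1.3.2).

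**Tables.** SAP 3.4: "All safety analyses will be performed in the SS (resp. DLTES for DLT analysis) by treatment dose level combination and overall". The DLT output in SAP 3.4.1 is the "Number and percentage of patients with at least one DLT before the end of the first cycle". It has no separate lead-in line.

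**Protocol, dose-finding.** Section 10.2.6: "If a DLT occurred at LID1, the DLT will be considered as relative to 25 mg of S64315 in monotherapy", and "If a DLT occurred at LID2, the DLT will be considered as relative to 50 mg of S64315 in monotherapy". It adds that "the patient will be replaced to ensure the minimal number of patients needed in the cohort at the full tested dose", and that these DLTs are still taken into account at the end-of-cohort meeting.

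**Protocol, reporting.** Section 10.4.4.2 tabulates DLTs from the lead-in to the end of cycle 1, by dose level and overall. It does not say which dose level a lead-in DLT falls under.

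**The concern.** The lead-in is identical whichever cohort is open, so a lead-in-only patient carries no information about the full dose of that cohort. Under the SAP rule, the same lead-in DLT would appear under 50, 100, 200 or 250 mg plus azacitidine, depending only on when the patient enrolled. In the 25 mg column, a patient who had reached LID2 would have received twice the labelled dose.

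Such patients are foreseeable. Protocol 2.3.6 says the lead-in is partly there to detect cardiac sensitivity before higher doses are given. The DLT criteria also count a drug-related failure to receive LID2, or to start cycle 1, as a DLT.

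The abbreviated report contains no efficacy analysis, and the primary objective is safety, including DLTs and the MTD. A reader should therefore be able to trace the DLT counts by dose to the protocol's attribution. As planned, that may not be possible.

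**Working it through.** There is no sample size, power or error rate to reproduce, because the question is one of attribution. The check has three steps.

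**1. Who can enter the DLT table (SAP 2.1, DLTES).**
- The first criterion excludes patients who stopped before C1D28 for a reason other than a DLT. A lead-in-only patient without a DLT is therefore out.
- The third criterion (minimum exposure) has an exception for stopping because of a DLT. A lead-in-only patient with a DLT passes both.
- The second criterion excludes anyone without a DLT assessment at the end of cycle 1, and it has no such exception. Read literally, it could remove the lead-in DLT patient.
- Protocol 10.2.6 points the other way: a DLT in the lead-in is an accepted alternative to the minimum exposure when a cohort is evaluated.

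Inclusion is therefore the more natural reading, but it is not certain.

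**2. Effect on the by-dose DLT rate if included.** Let n be the evaluable patients who received the full dose, x those with a DLT, and k the lead-in-only DLT patients placed in the same column. The values n = 3 and n = 6 are the minimum and the initial maximum of evaluable patients per dose level. The values of x and k are assumptions, since the documents give no counts.

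- Rate under the protocol's attribution: x/n
- Rate under the SAP's columns: (x + k)/(n + k)
- Difference: k(n − x) / [n(n + k)], which is never negative and is zero only if k = 0 or x = n

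| n | x | k | Protocol attribution | SAP column |
|---|---|---|---|---|
| 6 | 0 | 1 | 0/6 = 0% | 1/7 = 14.3% |
| 6 | 1 | 1 | 1/6 = 16.7% | 2/7 = 28.6% |
| 6 | 1 | 2 | 1/6 = 16.7% | 3/8 = 37.5% |
| 3 | 0 | 1 | 0/3 = 0% | 1/4 = 25.0% |

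For the second row, the difference is 1 × 5 / (6 × 7) = 5/42 = 11.9 percentage points.

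If the patient is instead excluded under the literal reading, the column returns to x/n, but the lead-in DLT disappears from the DLT table. It also disappears from the DLT listing, which SAP 3.4.1 restricts to the same set. Neither reading shows the DLT where protocol 10.2.6 puts it.

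**3. Effect on the other safety tables.** In the Safety Set a lead-in-only patient may or may not have a given event, so the shift can go either way. With 3 of 6 full-dose patients affected (50.0%), one lead-in-only patient gives 3/7 = 42.9% without the event or 4/7 = 57.1% with it.

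**The case against.** Several points against the concern stand.

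- **The 25/50 mg attribution governs dose-finding.** A reader might infer that the SAP contradicts the protocol. It does not break a stated tabulation rule: 10.4.4.2 asks for lead-in and cycle 1 DLTs together by dose level and is silent on the dose for a lead-in DLT.
- **Every column already includes the lead-in.** The SAP's treatment period starts at the first IMP intake, so lead-in AEs of patients who reached cycle 1 also sit in their full-dose column. The columns describe a regimen of lead-in plus assigned dose, and grouping by assigned cohort is defensible for that.
- **Removing lead-in-only patients has a cost.** AE columns without them would be limited to patients who tolerated the lead-in. A reader might infer that these patients should be moved out of all by-dose tables, but the documents do not support that as a clear improvement.
- **The number affected is unknown.** If there were none, nothing changes. SAP 3.1 also limits percentages to dose levels with enough patients, although the counts would still differ.
- **Some of the information is planned elsewhere.** Disposition is given separately for the lead-in and each cycle, and exposure by planned dose includes the number of patients reaching each. The table shells are a separate document and may already carry footnotes.

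These points remove most of the force for AE, laboratory, ECG and LVEF tables. They do not settle the DLT table. Disposition and exposure show who stopped in the lead-in, but the SAP text does not say that the DLT table or listing will identify which DLTs arose there.

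**Conclusion.** The point holds for the DLT table. As written, the SAP either places a lead-in DLT under a combination dose that was not given or, on the literal reading of its evaluability criteria, may drop it. If included, one such patient in a column of six raises the rate by 14.3 percentage points from 0/6, or by 11.9 points from 1/6. These sizes assume one lead-in-only DLT patient per column and are illustrations.

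For the other by-dose safety tables the need is for labelling, because the planned-cohort grouping is a legitimate convention when it is stated.

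A reader might infer that dose decisions were affected. The documents give no support for that: the model rule in protocol 10.2.6 is untouched by the SAP, lead-in DLTs were to be considered at the end-of-cohort meetings, escalation has stopped, and no expansion will follow. The choice of column also leaves the overall rates unchanged.

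**What to change.** **DLT table (SAP 3.4.1).**
- Report lead-in DLTs on separate lines: LID1 as 25 mg S64315 alone, and LID2 as 50 mg S64315 alone.
- Limit the by-dose rate at the full tested dose to evaluable patients who received S64315 at C1D2.
- Mark each DLT in the listing as lead-in or cycle 1.

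**DLTES (SAP 2.1).** State that a patient with a lead-in DLT stays in the set despite having no end-of-cycle-1 assessment.

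**Other by-dose safety tables.**
- Keep the planned-cohort grouping and label the columns as lead-in plus assigned dose.
- Give the number of lead-in-only patients in each column.
- A separate lead-in-only column is optional, as a sensitivity display.

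**Cost.** A few extra table lines and footnotes, with no new data. The full-dose DLT columns will no longer sum to the overall column without the lead-in lines, so a footnote should say so.

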Creatine kinase (CK) / Creatine phosphokinase (CPK)	Grade ≥ 3 serum CK/CPK Grade 3 isolated electrolyte abnormalities (i.e. those occurring without clinical consequence) not recovered with or without intervention, to Grade < 2 level within 72 hours

TOXICITY	DLT CRITERIA
Electrolyte abnormalities (including magnesium, calcium, phosphorus, etc.) clinically significant	Any Grade 4 electrolyte abnormality
Cardiac disorders	QTcF interval \geq 501 ms or increase of $>$ 60 ms from baseline on at least two separate ECG assessments (1 assessment = triplicate ECG) Asymptomatic, absolute decrease in LVEF of 10% or greater from baseline AND LVEF $<$ 50% Asymptomatic, absolute decrease in LVEF of 20% or greater from baseline Troponin increase $>$ 10xULN or a troponin increase consistent with the diagnosis of a myocardial infarction (Grade 3) Symptomatic congestive heart failure
Skin and subcutaneous tissue disorders	Grade \geq 3 rash
Haematological abnormalities	Grade 4 neutropenia and/or thrombocytopenia persisting for 28 days after the start of azacitidine dosing in a cycle of therapy in the absence of active AML ($<$ 5% blasts) or active MDS or myelofibrosis
Other AEs	Any Grade \geq 3 AE Single event or multiple occurrences of the same event that lead to a dosing delay of $>$ 7 days in a cycle may be considered to be DLT by the Investigators and the Sponsor, even if not Grade \geq 3 Failure to restart test drug administration at the same dose due to drug-related toxicity Failure to restart test drug administration at the same dose within one cycle (i.e. 28 days) of the first missed dose due to delayed recovery from drug-related toxicity Failure to initiate cycle 1 after completing the LID period or failure to receive LID2 after receiving the LID1, due to drug-related toxicity
NCI CTCAE v5.0 will be used for grading	

The following criteria will not be considered as DLT:

- Grade 3 nausea, vomiting, diarrhoea, anorexia or constipation that do not result in hospitalization, tube-feeding or use of TPN
- Grade 3 fatigue, asthenia, fever
- Grade 3 isolated electrolyte abnormalities (i.e. those occurring without clinical consequence) that resolve, with or without intervention, to Grade $<$ 2 level in 72 hours

Patients who meet any of the criteria included in Table (4.1.3.5) 2 at the end of Cycle 1 will not be evaluable for DLT and therefore will be replaced during the dose escalation phase I part of the study, but not in the expansion parts of the study.

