5.8. Patient withdrawal

5.8.1. Withdrawal criteria

Information to be collected during the last visit of these patients is given in [section 5.8.2](#). These follow-up modalities are used to ensure the efficacy and safety evaluation of all patients who received the IMPs.

The reasons for premature discontinuation of IMPs are:

- **Adverse events** incompatible with continuation of one of the IMPs according to the judgment of the investigator, including no recovery in safety parameters. Criteria for treatment discontinuation are implemented during the LID period in order to avoid treating a patient in medical condition that could jeopardize his/her safety or interfere with the conduct of the study. If the patient cannot receive the LID2 or the first S64315 C1D2 dose due to an AE, the S64315 infusion (either LID2 or C1D2) may be postponed by 1 to 5 days. If the LID2 is postponed for more than 2 days (5 days maximum), the C1D2 dose may not be postponed for more than 2 days. If S64315 C1D2 is postponed, azacitidine C1D1 dose should be postponed as well, whenever possible. If the AE has not recovered within this time period, the patient must be withdrawn from the study.
- **Pregnancy** (for reporting, see [section 8.9.2.3](#))
- **Protocol deviation** if it interferes with the study evaluations and/or if it jeopardises patient's safety, e.g. any medical event requiring administration of an unauthorised concomitant treatment (see [section 6.3](#))
- **Disease progression** at the discretion of the investigator
- **Treatment failure**, defined as failure to achieve CR, CRi, MLFS or PR after at least 6 cycles of study treatment
- **Non-medical reason** (to be thoroughly described) e.g. consent withdrawal, patient's removal
- **Other, physician decision** (for reasons that cannot be included in any of the criteria listed above, for example: availability of a better therapeutic alternative for the patient)

If the patient becomes eligible for transplant, patient treatment discontinuation should be left to the investigator's decision.

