5.8.2. Procedure

Upon discontinuation of the IMPs, the investigator must:

- notify the Sponsor immediately by recording this information in the eCRF
- indicate the main reason, if there are several reasons

Patients should return for the Withdrawal visit (WV) as soon as possible and up to 28 days of the last dose of IMP. If the decision to discontinue occurs at a regular scheduled visit, that visit may become the WV rather than having the patient returns for an additional visit.

After the withdrawal visit, patients will continue in the follow-up period; the date of death and the progression date will be recorded in the eCRF, if applicable. Study discontinuation for another reason than disease progression will be recorded in the eCRF.

In the case of premature withdrawal from the study due to an AE (event requiring immediate notification or not), the investigator must make every effort to collect the information relating to the outcome of the AE. If necessary, the information will be collected afterwards (see [section 8.9](#)). This information is recorded in the 'AEs' eCRF form. If the investigator cannot collect the information during a patient visit, he must collect it from the patient's doctor in charge of his/her follow-up.

If the study is stopped/one of the IMPs is discontinued as a result of an event requiring immediate notification, the procedure described in [section 8.9.2.5](#) is to be implemented.

The dispositions to be taken after the IMPs discontinuation are described in [section 6.5](#).

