8.2.5.3. Cardiac marker follow-up

In order to monitor a potential cardiac toxicity, a cardiac marker assessment, including troponin, CPK-MB and BNP, will be performed at predose, 6h, 24h, 48 and 72h after S64315 EoI on the days of LID1 (D-13) and LID2 (D-6), C1D2 and C1D9 and at each pre-dose assessments for the following visits.

Either troponin I or T assessment can be used, but it should be ultra-sensitive, whenever possible. The same subtype (either I or T) should be used throughout the study. If, for a given centre, both troponin I and T can be assessed, priority should be given to troponin I.

In case of troponin increase observed after any of the first two S64315 infusions during cycle 1 (C1D2 or C1D9), it will be recommended to assess these cardiac markers at 48h and 72h S64315 EoI and after each subsequent S64315 infusions (before discharge and beyond, if needed) on a regular basis according to the investigator's judgment.

In case of troponin increase $> 10\times\text{UNL}$ or a troponin increase consistent with the diagnosis of a myocardial infarction (Grade 3), the patient should discontinue study treatment (see [section 8.12](#)).

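### The end-of-cycle-1 assessment criterion has no DLT exemption, so as written it drops lead-in DLT patients who never start cycle 1 from the primary DLT table

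*SAP*

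**What the plan says.** SAP 2.1 defines the DLTES, and SAP 3.4.1 builds both the DLT table and the DLT listing on it. The grounds for non-evaluability are taken from protocol Table (4.1.3.5) 2:

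- Permanent discontinuation before C1D28: DLT is exempted.
- "Did not undergo a DLT assessment at the end of Cycle 1": no exemption.
- Less than the minimum exposure: a stop for DLT is exempted.
- More than the assigned doses received: reassessed case by case.

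Protocol 4.1.3.5 says how these combine: "Patients who meet any of the criteria included in Table (4.1.3.5) 2 at the end of Cycle 1 will not be evaluable for DLT".

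The same section lists as a DLT "Failure to initiate cycle 1 after completing the LID period or failure to receive LID2 after receiving the LID1, due to drug-related toxicity", and SAP Table (4.2.3.1) 1 repeats it. For a lead-in adverse event that delays dosing, protocol 5.8.1 adds: "If the AE has not recovered within this time period, the patient must be withdrawn from the study".

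The first primary endpoint in SAP 1.2 is DLT incidence counted from the lead-in period. Protocol 10.4.4.2 likewise tabulates DLTs from the lead-in to the end of cycle 1 in the DLTES. Protocol 10.4.3.1 defines that set by reference to section 4.1.3.6, which is DLT management and holds no evaluability criteria; they are in 4.1.3.5.

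**The concern.** The second criterion works against the endpoint. The plan names a lead-in failure as a DLT and starts the endpoint window at the lead-in, yet it makes evaluability depend on an assessment that such a patient cannot have. The exemptions beside it do not help, because one unmet condition is enough to exclude.

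At stake is the main safety figure of the report. Excluding a DLT patient removes one case from the numerator and one from the denominator, so the error has one direction. It falls on the toxicities that stop treatment earliest. Protocol 2.3.6 gives early detection of cardiac sensitivity as one purpose of the lead-in, so the events lost could be those it was meant to reveal.

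**Working it through.** The plan gives no figure for this point, so there is none to reproduce. The check is a reading of the rules followed by simple proportions.

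**Step 1: DLT in the lead-in, cycle 1 never started.** Toxicity prevents LID2 or C1D2, which is a DLT by definition (protocol Table (4.1.3.5) 1). If it does not recover in time, the patient is withdrawn (5.8.1). The discontinuation criterion is not met, because the stop was for a DLT. The exposure criterion is not met, for the same reason. The assessment criterion is met, because there is no cycle 1 to end. One criterion suffices, so exclusion is certain on the wording.

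**Step 2: DLT stop within cycle 1.** As an example, protocol 8.2.5.3 says that for troponin above 10 x ULN or "a troponin increase consistent with the diagnosis of a myocardial infarction (Grade 3), the patient should discontinue study treatment"; the same finding is a listed DLT. Protocol 5.8.2 then says: "Patients should return for the Withdrawal visit (WV) as soon as possible and up to 28 days of the last dose of IMP". Nothing states that this visit counts as the end-of-cycle-1 assessment. However, protocol 4.1.3.5 calls for a DLT assessment in every patient at the end of cycle 1, and after a stop at C1D2 the 28-day visit window runs to day 2 + 28 = day 30, past C1D28. Exclusion therefore needs a further event: that no assessment is made.

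**Step 3: direction.** With r DLTs among n patients and k DLT patients excluded, the table shows (r - k)/(n - k) instead of r/n. Since (r - k)n <= r(n - k) whenever r <= n, the tabulated rate is never higher. It is strictly lower unless every patient had a DLT.

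**Step 4: size, lead-in DLTs.** Assumed data: six patients complete the lead-in and one of them has a cycle-1 DLT. The number of lead-in DLT patients who never start cycle 1 is not in the documents.

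| Lead-in DLTs | Lead-in plus cycle 1 | Tabulated as written |
|---|---|---|
| 0 | 1/6 = 16.7% | 1/6 = 16.7% |
| 1 | 2/7 = 28.6% | 1/6 = 16.7% |
| 2 | 3/8 = 37.5% | 1/6 = 16.7% |

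**Step 5: size, cycle-1 DLTs, only if not assessed.** 2/6 = 33.3% becomes 1/5 = 20% if one of the two has no assessment, and 0/4 = 0% if neither has.

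**Step 6: general form.** Let p be the true risk and q the share of DLT patients with no end-of-cycle-1 assessment. The tabulated rate is p(1 - q)/(1 - pq). The share q is not in the documents and is not the same as the share who stop early. For assumed q of 25%, 50% and 75%, a true 33% is shown as 27%, 20% and 11%, and a true 25% as 20%, 14% and 8%.

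**The case against.** The strongest reply is that the intent is plain. Protocol 10.2.6 lets a patient count for dose allocation if the minimum doses were given, or alternatively if the patient is one of those who "have had a DLT within the LID period or the first cycle". The sentence on replacing patients outside the DLTES follows directly, so this can be read as the DLTES rule. The exemptions in the neighbouring criteria would do little if every early DLT stop failed the middle one. Protocol 4.1.3.3 cites the right section for evaluability, so the wrong number in 10.4.3.1 can be traced. The patients would not vanish either: SAP 3.2.3 lists exclusions with reasons, SAP 3.2.1 shows withdrawals for the lead-in separately, and SAP 3.4.2 keeps the events in the adverse event tables.

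Most of this stands. A statistician who knows 10.2.6 would probably keep these patients. But the SAP does not repeat that alternative, and 10.2.6 is written for dose allocation. It also has lead-in DLT patients replaced (LID2 cases at least), and replacement is otherwise what happens to non-evaluable patients. Investigator reporting of DLTs (SAP 4.2.3.1) settles what is a DLT, not who is in the set. SAP 3.4.2 plans no breakdown by DLT status, so no planned DLT output would show the excluded patient's DLT.

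A reader might go further and infer that every patient who stops early for a DLT is lost. Step 2 shows that the documents do not support this.

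**Conclusion.** The criterion lacks an exemption that its neighbours have. As written, it certainly excludes patients with a lead-in DLT who never start cycle 1. It excludes cycle-1 DLT stops only when the end-of-cycle-1 assessment is not done. The DLT table and listing would then understate the rate; in the two-case illustration, 37.5% is shown as 16.7%. The counts in that example and the values of q are assumptions; the direction is not. The effect is confined to the reported DLT rate and listing.

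A reader might also infer that the dose-escalation model is at fault, since protocol 10.2.6 says "If a DLT occurred at LID1, the DLT will be considered as relative to 25 mg of S64315 in monotherapy" and treats LID2 in the same way at 50 mg, while the MTD is defined on lead-in plus cycle 1. The documents do not make that a defect. Booking an event to the dose received is defensible. Protocol 10.2.6 takes these DLTs to the end-of-cohort meeting, and Appendix 8, section 1.2.5, names them among the factors considered beyond the model. Escalation has stopped (SAP 1.3.1), and the SAP plans no model output.

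**What to change.** 1. Add *unless a DLT occurred during the LID period or Cycle 1* to this criterion in SAP 2.1 and in protocol Table (4.1.3.5) 2.
2. State in SAP 3.4.1 that lead-in DLT patients stay in the DLTES at their planned dose level, as SAP 2.1 already does for lead-in-only patients in the safety analysis. Footnote that the planned dose was not received. Show lead-in and cycle-1 DLTs separately and combined.
3. Correct the cross-reference in protocol 10.4.3.1 from 4.1.3.6 to 4.1.3.5.

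The cost is one clause in two documents, one section number, and one sentence with a split table and footnote. No new data are needed. The downside is that the reported DLT rate may be less favourable.
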